A robust literature documents the efficacy of cognitive behavioral therapy for insomnia (CBT-I) compared to control conditions.⁷ Additionally, mounting evidence has shown that CBT-I is associated with improved depression outcomes, including higher rates of depression remission among participants with insomnia and depression,⁸ and lower depression symptom severity among non-pregnant adults with both insomnia and subclinical depression symptoms compared to digital attention-matched placebo control.⁹ In a single group study, participants reported significant improvements in subjective and objective sleep parameters and depression symptom severity after five weekly sessions.¹⁰ These results are promising, but the trial lacked a control group and therefore does not support causal inference.

Qualitative research shows that women report a preference for mental health care that includes flexible options. ¹¹ Thus, digital programs may be of particular interest during the perinatal period. A recent meta-analysis supports the efficacy of digital CBT-I for sleep compared to control. ¹² Sleepio is a digital CBT-I program associated with significantly greater improvements in sleep efficiency (among other sleep parameters) and depression symptom severity compared to both active control and treatment as usual conditions immediately post-intervention and at an 8-week follow-up. ^{13,14} The overarching goal of this project is to use a randomized control design to examine the efficacy of digital CBT-I (Sleepio) for sleep and mental health outcomes compared to treatment as usual among pregnant women with insomnia symptoms.

Objectives

- **Aim 1**: To test the hypothesis that participants randomized to digital CBT-I will demonstrate significantly greater improvements in subjective sleep outcomes, including insomnia symptom severity (primary outcome), sleep duration, sleep efficiency, global sleep quality, and insomnia caseness, compared to TAU participants.
- **Aim 2**: To test the hypothesis that participants randomized to digital CBT-I will experience significantly greater improvements in mental health outcomes, including depressive symptoms (primary) and anxiety symptoms, compared to TAU participants.

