Outcomes. The primary outcome is change in insomnia symptom severity (Insomnia Severity Index) from baseline to 10-weeks post-randomization. Secondary sleep outcomes include sleep efficiency (sleep diary), sleep duration (sleep diary), global sleep quality (Pittsburgh Sleep Quality Index), and insomnia caseness (Sleep Condition Indicator). Secondary mental health outcomes include depressive symptom severity (Edinburgh Postnatal Depression Scale) and anxiety (Generalized Anxiety Disorder Scale). We will additionally examine change to 18-weeks post-randomization, 36 weeks gestation, 3 months postpartum, and 6 months postpartum. Other, exploratory outcomes include birth outcomes, such as gestational age at delivery, APGAR scores, birthweight, and delivery method.

Participant timeline (See Figure). *Eligibility survey.* Individuals interested in participating will complete an electronic consent form describing the screening procedures. Next, participants will complete questionnaires to assess eligibility. Participants will complete a demographic measure, provide contact information, and indicate whether they agreed to be contacted for other research studies. Individuals who pass the eligibility survey will complete the study consent form and be given instructions to complete the sleep diaries.

Sleep diaries. Participants will receive email requests to complete sleep diaries on REDCap for seven consecutive days. Participants will indicate when they got in bed, how long it took to fall asleep, number of awakenings, duration of awakenings, final awakening time, and when they got out of bed. Participants who complete at least four diaries will be eligible to proceed to the orientation session.

Orientation. The primary goal of the phone orientation session, modeled after Goldberg and Kiernan (2005),¹⁵ is to promote participant retention by discussing the importance of the trial, required commitments, what to expect if randomized to digital CBT-I or TAU, the rationale of the control condition and random assignment, and the impact of attrition bias. Participants will describe personal pros and cons for participating in the trial, and will be given as much time as needed to decide whether to participate.

Baseline measures. Participants will complete baseline measures on the Qualtrics online survey system.

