Randomization. Upon the participant's completion of the baseline measures, study staff will request the condition assignment from the independent investigator who generated the randomization sequence. Study staff will inform participants of their condition assignment by phone call and email.

Follow-up assessments. Participants will complete all study measures and the daily sleep diaries at 10-weeks post-randomization, and all study measures at 18-weeks post-randomization, 36 weeks gestation, 3 months postpartum, and 6 months postpartum.

Sample size. Existing literature comparing CBT-I to treatment as usual suggests a large effect size (Cohen's d=0.95) for baseline to post-intervention differences and a medium effect size (Cohen's d=0.69) for baseline to 8-week follow-up on sleep efficiency.¹³ As for depression symptom severity, existing literature comparing CBT-I to treatment as usual suggests a small to medium effect size (Cohen's d=0.20-0.69) for baseline to post-intervention differences and a medium effect size (Cohen's d=0.48-0.78) for baseline to 8-week follow-up.^{9,14} Using G*Power for an ANOVA repeated measures with a within-between interaction, we estimated that 128 women were required to have 80% power to detect a small-to-medium effect size (Cohen's d=.30) with α =.01 for a within-between interaction. Attrition in web-based CBT-I programs ranges from 4-22%.^{13,16,17} but a meta-analysis of computer-based treatments for depression estimated drop-out rates of 38.4% in programs that offer administrative support. ¹⁸ We used the higher attrition estimate of 38%, yielding a required sample size of 208 participants (n=104 per group).

Recruitment. We will utilize several recruitment methods to meet our target sample size. Although recruitment will focus mainly on the Bay Area, participants can enroll from anywhere because all study activities are completed remotely.

UCSF Outpatient Recruitment Program. Study recruiters will review medical records of women receiving prenatal care at UCSF. Women who may be eligible based off chart review (e.g., less than 28 weeks pregnant) will be approached in the clinic waiting area at the time of their appointment to be introduced to the study. Recruiters will give the patient an opt-in card

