Participants will be sent reminders via their preferred method of communication after 3, 5, and 10 days of non-response. After 2 weeks of non-response, we will contact their secondary contact person. After 3 weeks of non-response, we will mail the primary outcome measure with a stamped and addressed return envelope. Every effort will be made to obtain outcome data from

participants who discontinue the intervention. If need be, participants who discontinue the intervention can opt to only complete the primary outcome measure to reduce time burden.

Data management. Qualtrics maintains data behind a firewall. All data is accessed only by the owner of the survey who must provide a user ID and a password. All pieces of data are keyed to that owner identification and cannot be accessed by anyone else.

REDcap is housed in a locked and guarded data center staffed at all hours. Entrance to the data center requires use of a card key to unlock the data center door and a second card key lock secures the cage that the servers reside within. The security of the data center is further protected by an Operations desk that is staffed 24x7 and by a security camera system. REDcap servers are guarded by multiple firewall and intrusion detection systems. All electronic connections to the REDcap environment are encrypted. The REDcap production system is comprised of a web server front-end and a MySQL database server back-end. The web server resides in a demilitarized zone to ensure that survey participants are able to access REDcap surveys from any device connected to the Internet. The MySQL server back-end resides in the protected ISU subnet that is protected by UCSF maintained firewalls. The data stored in the REDcap MySQL database server can be accessed by the REDcap end users by logging in and opening the REDcap project(s) that they have been granted access to by the owners of the projects. Only ITS and ISU system administrators are authorized to access the back-end database server directly by logging into the virtual private network for the database server resides in.

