Statistical methods. Independent samples t-tests and chi-square tests will be used to examine between-group differences in baseline sociodemographic and clinical characteristics. Linear mixed effects models will be used to examine whether within-woman changes in sleep and mental health outcomes differ between the digital CBT-I and treatment as usual groups. 30 Models will include the sleep and mental health outcomes as the dependent variables, along with time, intervention group, and time by group interactions as the predictors. The models also will include random intercepts to accommodate the correlation among the repeated responses within women. The regression coefficients of time by intervention group interactions measure the differences in the rate of within-woman change in the outcomes between the two intervention groups. We will assess the statistical significance of the time by intervention group interaction using likelihood ratio tests. The primary analysis will assess differences in changes in insomnia symptom severity from baseline to post-intervention with time measured in weeks. Secondary analyses of additional sleep and mental health outcomes will use the same time scale. Additionally, we will examine change from baseline to follow-up.

Monitoring

Harms. Adverse events that are spontaneously reported by participants will be characterized by an independent safety officer as unexpected or expected, and causes will be characterized as definitely related, probably related, possibly related, or unrelated to study participation. Adverse events that are determined to be unrelated to study participation are documented but not reported to the IRB. All other adverse events are reported to the IRB.

Ethics and Dissemination

Research ethics approval

The research protocol will be submitted to the UCSF institutional review board for approval.

Protocol amendments

Protocol modifications will be communicated to all study investigators and approved by the IRB prior to implementation, and the trial registry will be updated accordingly.

Consent or assent

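### Yes/no insomnia caseness is assigned to a linear mixed model, whose test rejects too often if about 90% or more of women are cases at entry and loss is substantial

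*Combined protocol and SAP*

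**What the plan says.** Aim 1 lists the secondary sleep hypotheses as "sleep duration, sleep efficiency, global sleep quality, and insomnia caseness, compared to TAU participants", and the Outcomes section names "insomnia caseness (Sleep Condition Indicator" among the secondary sleep outcomes. The Data collection methods section uses the SCI to identify possible DSM-5 cases, so the outcome is yes/no.

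The Statistical methods section is the only efficacy analysis text. It states: "Linear mixed effects models will be used to examine whether within-woman changes in sleep and mental health outcomes differ". It adds: "The models also will include random intercepts to accommodate the correlation among the repeated responses within women". The test is a likelihood ratio test of time by group, with time in weeks, and "Secondary analyses of additional sleep and mental health outcomes will use the same time scale". Caseness is not exempted. No logistic, binomial, GEE or robust-variance method appears, and chi-square tests are named only for baseline characteristics.

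Two other passages bear on missing SCI data. The Sample size section says "We used the higher attrition estimate of 38%, yielding a required sample size of 208 participants (n=104 per group". The Data collection methods section says "participants who discontinue the intervention can opt to only complete the primary outcome measure to reduce time burden", and the questionnaire mailed after three weeks of non-response is the primary outcome measure.

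**The concern.** A random-intercept linear model normally assumes one residual variance at all visits. The variance of a 0/1 variable is p(1 - p), which shrinks as p nears 1. Entry selects women with insomnia symptoms, so most may be cases at baseline, while fewer should be at 10 weeks. Women with only a baseline SCI stay in the model and give extra weight to the low-variance visit. The pooled variance can then fall below the 10-week variance that governs the treatment comparison, making the standard error too small.

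At stake are the error rate and confidence interval of a named Aim 1 outcome. The result would also be expressed as a difference in weekly change of a 0/1 variable, which is awkward to interpret.

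**Working it through.** **Inputs from the plan.** 208 randomised, 104 per arm; 38% planned loss; cited range for web-based CBT-I of 4-22%; alpha .01 in the Sample size section and none stated for the analyses. Entry is by SCI or by ISI of 11 or more, so baseline caseness may be below 100%.

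**The plan's own figure.** No figure is given for caseness. For the repeated-measures calculation (d = .30, so f = .15; two visits; correlation .5 assumed; alpha .01), 128 women give 78.0% power, within 2 points of the stated 80%. 128/0.62 = 206.5 and 128/0.616 = 207.8, so 208 fits the 38.4% drop-out figure. This leaves about 64 per arm at 10 weeks.

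**Assumed.** Baseline caseness of 50-100%; 10-week caseness of 50-70% without an effect, and 65% v 40% with one; latent within-woman correlation .3-.7; dropout at random.

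**Mechanism at 90% baseline caseness.** Baseline variance is .90 × .10 = .09; 10-week variance at 52.5% caseness is .525 × .475 = .249. Pooled over 104 and 64 values: (104 × .09 + 64 × .249)/168 = .151, about 61% of the 10-week variance.

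**Closed form at 100% baseline caseness.** With n women per arm seen at 10 weeks and 10-week variance v, pooled variance is v × n/(104 + n). The model's variance for the difference in change is 2 × pooled × (1/104 + 1/n) = 2v/104; the true variance is 2v/n. The test statistic is therefore inflated by √(104/n):

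- 38% loss, n = 64: √1.625 = 1.275; 1.96/1.275 = 1.537; type I error 12.4%.
- 22% loss, n = 81: 1.133; 1.730; 8.4%.
- 4% loss, n = 100: 1.020; 1.922; 5.5%.
- No loss, n = 104: 1.000; 5.0%.

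**Simulation, 10,000 trials per setting, alpha .05, 38% loss.** Two separate simulations with different assumed rates. Set A has 10-week caseness of 52.5% or 65% in both arms; set B has 70%, with 50% in brackets. Coverage is from set A.

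| Baseline caseness | Type I error, A | Type I error, B | 95% CI coverage |
|---|---|---|---|
| 60-75% (B: 70%) | close to nominal | 5.1% (6.1%) | 94-95% |
| 90% | 8.0-8.5% | 7.6% (8.5%) | 92% |
| 95% | 9.6-10.4% | 9.4% (10.3%) | 90% |
| 100% | 11.8-13.0% | 12.6% (13.4%) | 88% |
| Logistic at 10 weeks | 4.8-5.6% | 4.4-5.4% | 94-95% |

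A further check gave about 6-7% at 60-75%. At alpha .01, set A gives 2.2-2.4% at 90% and 4.1% at 100%, against 0.9-1.2% for logistic regression. At 22% loss, set A gives 6.3-7.1% at 90% and 8.6-10.5% at 100%. At 4% loss, the rate is 4.9-6.3% for baseline caseness of 90-100%. With complete pairs only, it is 4.8-5.7% at 60-95% and 5.1-6.2% at 100%.

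**Point estimate.** Ten times the weekly coefficient averages the true -25 points. The fault is in the standard error: its mean against the true standard deviation of the estimate is .100 v .101 at 60% baseline caseness, .081 v .090 at 90% and .067 v .086 at 100% (correlation .3).

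**Power, 38% loss, 65% v 40%.** Planned test against baseline-adjusted logistic regression, at correlations .3, .5 and .7: 71 v 84%, 76 v 86% and 85 v 90% at 60% baseline caseness; 74 v 83%, 80 v 86% and 86 v 89% at 75%. For a continuous outcome with equal variances, a change score has 2/(1 + ρ) times the variance of an adjusted comparison. At ρ = .5 this is 1.333, so 84% adjusted power (1.96 + .99 = 2.95 standard errors) becomes 2.95/√1.333 = 2.56, or about 73%. The power gap is therefore not peculiar to 0/1 data.

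**The case against.** Inflation needs several unstated conditions together: baseline caseness near 90% or more, substantial loss, baseline-only women kept, and a single residual variance with model-based tests. The plan never says the variance is constant; that is the standard form of the model it describes. The 38% comes from computer-based depression treatments, and for this kind of programme the protocol says "Attrition in web-based CBT-I programs ranges from 4-22" percent. At 4% loss the test is sound. This stands and limits the claim, but 38% is the loss the trial planned for, and 22% loss still gives 6-7% at 90% baseline caseness.

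The diagnosed fault is in the standard error, and a sandwich standard error on the planned model largely repairs it: 4.5-5.8% at 90-95% baseline caseness and 5.4-6.5% at 100%, at 38% loss. This also stands, so it is offered below as the minimum correction.

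A reader might infer that the interval is too narrow whenever most women are cases. The figures do not support that: coverage is 94-95% at 60-75%. Nor is the estimate biased when dropout is at random. Missing SCI data could differ by arm, since the ISI-only option is for women who discontinue the intervention, and neither method repairs dropout that depends on the unseen outcome.

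**Conclusion.** The concern holds in a limited form. The plan assigns a yes/no outcome to a linear model and names no binary method. At 38% loss, type I error at alpha .05 is about 8%, 10% and 12-13% at baseline caseness of 90%, 95% and 100%, with coverage of 92%, 90% and 88%. At 22% loss it is about 6-7% at 90% and 8-10% at 100%. At 4% loss, with complete pairs, or at 60-75% baseline caseness, it is close to nominal. These results rest on assumed caseness rates and correlations, dropout at random, and the standard form of the model.

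Separately, at 60-75% baseline caseness the change contrast gives up power, for example about 76 v 86% at 60% with correlation .5. That is a general property of the contrast, which the ISI analysis shares. A reader might infer that the primary result is invalid; the documents do not support this, because the error-rate problem arises from the 0/1 variance. The text should be changed, but the matter concerns one secondary outcome.

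**What to change.** In Statistical methods, exempt caseness from the linear mixed model.

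- **10 weeks:** logistic regression on group, adjusted for baseline caseness where it varies. Report the risk difference standardised over the women analysed, and the odds ratio, with 95% confidence intervals.
- **Later visits:** one named binary model on post-baseline visits only, for example a logit GEE with robust standard errors, with categorical visit, group by visit and baseline caseness as a covariate.
- **Avoid** a logit time-by-group model with baseline as a response. At 38% loss and 95% baseline caseness its power for 70% v 50% fell to about 22%, against about 66% for the 10-week logistic comparison, and at 100% it cannot be estimated.
- **Minimum alternative:** if the common linear model is kept, use robust (sandwich) standard errors for caseness.
- **Minor:** Eligibility criteria relax the symptom-duration rule to one month, while Data collection methods do not say which duration defines outcome caseness. Reconcile the two and use one rule at every assessment. This affects both arms alike.

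The cost is SAP wording, with no new data. Caseness no longer shares the common model form, women with baseline data only do not contribute, and an unweighted GEE needs a stronger missing-data assumption than a likelihood model.

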- **Aim 3**: To explore the impact of digital CBT-I on birth outcomes. In response to research indicating that insomnia and poor sleep quality are associated with increased risk for preterm birth, we will compare rates of preterm birth, as well as other birth outcomes such as low birthweight, delivery method, and APGAR scores, between digital CBT-I and TAU participants. Because the sample size of the proposed study will be too small to draw conclusions, this aim is exploratory.

Trial Design

The study is a parallel group, superiority, randomized controlled trial of digital CBT-I versus TAU among pregnant women, with a 1:1 allocation ratio.

Methods

Participants, interventions, and outcomes

Study setting. All study activities will occur remotely via phone, website, and digital app.

Eligibility criteria. Inclusion criteria are: 1) self-reported pregnancy up to 28 weeks gestation, 2) 18 years of age or older, 3) meets DSM-5 criteria for insomnia disorder as determined by the Sleep Condition Indicator (women experiencing symptoms \geq 1 month are eligible in contrast to DSM-5 criteria requiring symptom duration \geq 3 months) or experiencing elevated insomnia symptom severity as determined by a total score \geq 11 on the Insomnia Severity Index, and 4) has regular access to a web-enabled computer, tablet, or smart phone. Exclusion criteria are: 1) probable major depression as determined by a total score \geq 15 on the Edinburgh Postnatal Depression Scale (EPDS), 2) self-reported bipolar disorder, 3) self-reported history of psychosis, 4) active suicidality defined as scoring > 1 on EPDS item 10, or report of a specific suicide plan or recent attempt, and 5) shift work employee.

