Electronic health record recruitment. MyChart (APeX) will conduct a search for patients based on the study's inclusion and exclusion criteria. This is a completely computer-aided search, meaning the computer— not a person— searches patient charts. When a patient is identified as potentially eligible, they will receive an email from MyChart that asks them to log in to MyChart to read about a study in which they might be interested. The email is short and is the same for every recipient—it contains no patient-specific or study-specific information. When the patient logs into MyChart, there will be a "Research" tab with template information about research participation and how to opt out of receiving recruitment messages. The patient can click through to learn about the specific study to which they have been matched. The patient has the option of clicking a button to let the study team know that they are interested in learning more about the study. The study team will only receive information about the patient if the patient takes this action. If the patient clicks "No thanks" or simply does not respond, they will not be contacted by the study team or receive any follow-up emails from MyChart about the study, nor will their information be shared with the study team.

Assignment of interventions

Allocation. The blocked randomization sequence will be generated by an independent investigator using Sealed Envelope.²⁰ The randomization sequence and block sizes will be concealed from study staff. The randomization sequence will be kept on an electronic file inaccessible to the study staff. Once a participant completes baseline measures, study staff will request the allocation assignment from the independent investigator. Study investigators and staff will not be able to influence randomization or have access to future allocations.

Blinding. For study administration purposes, staff will be unblinded to participant condition assignment after allocation. Study staff will be blinded to outcomes during the trial. Participants will be unblinded to condition assignment due to the nature of the comparison group, which is not an active comparator. The study statistician will remain blinded to condition assignment for all primary analyses.

Data collection, management, and analysis

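### Gestational age at entry is left out of the outcome models; prespecifying it with its time interaction is a low-cost efficiency improvement, not the correction of an error

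*Combined protocol and SAP*

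**What the plan says.** All references are to the combined protocol and SAP.

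- **Eligibility criteria:** the first inclusion criterion is "self-reported pregnancy up to 28 weeks gestation". No lower limit is given.
- **Trial Design and Allocation:** allocation is parallel-group "with a 1:1 allocation ratio". "The blocked randomization sequence will be generated by an independent investigator using Sealed Envelope". No stratification factor is named.
- **Statistical methods, model:** outcomes are modelled "along with time, intervention group, and time by group interactions as the predictors". A random intercept for each woman handles the dependence between her measurements. No baseline covariate is listed.
- **Statistical methods, primary contrast:** the analysis concerns "changes in insomnia symptom severity from baseline to post-intervention with time measured in weeks". The other outcomes use the same time scale, and change to follow-up is also examined.
- **Statistical methods, baseline:** "Independent samples t-tests and chi-square tests will be used to examine between-group differences in baseline sociodemographic and clinical characteristics". The text ties these tests to no adjustment or decision.
- **Follow-up assessments:** visits fall 10 and 18 weeks after randomization, at 36 weeks gestation, and at 3 and 6 months postpartum.

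**The concern.** Time is counted from randomization, but women start at different points in pregnancy. A woman who enters at 8 weeks has her primary assessment at 18 weeks gestation; one who enters at 28 weeks has it at 38. If untreated change in insomnia differs between those stretches, the model has no term to absorb the difference, and it adds to the residual variance of the treatment contrast. The trial already holds the variable: gestation is needed for eligibility and to schedule the 36-week visit.

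The later visits make the point more sharply. A woman entering at 28 weeks reaches 36 weeks gestation at week 36 − 28 = 8, before her 10-week visit, and her 18-week visit would fall at 28 + 18 = 46 weeks, after delivery. For a woman entering at 18 weeks, the 18-week and 36-week-gestation visits coincide (18 + 18 = 36). Entry gestation thus decides whether the 18-week visit is prenatal or postnatal, and where the 36-week visit sits on the weeks axis.

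At stake is some avoidable imprecision in the primary comparison, and a clearer reading of the later visits.

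**Working it through.** **Inputs from Sample size.** Cohen's d = 0.30, α = 0.01, a within-between interaction from G*Power, and "we estimated that 128 women were required to have 80% power"; 38% attrition; 208 randomized. The number of measurements m and their correlation ρ are not stated. I assume m = 2 (the primary contrast has two visits) and G*Power's default ρ = 0.5.

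**1. The plan's own figure.** With f = d/2 = 0.15, the noncentrality is λ = f²·N·m/(1 − ρ) = 0.0225 × 128 × 2/0.5 = 11.52 on (1, 126) degrees of freedom. At α = 0.01 this gives 78.0% power, within 2 points of the stated 80%. Solving for 80% gives N = 134. The unstated inputs can explain the gap: three measurements with ρ = 0.4 give 126. For attrition, 128/(1 − 0.38) = 206.5, rounded up to 207, and 128/(1 − 0.384) = 207.8, rounded up to 208. The plan's figures are reproduced closely enough to serve as a base.

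In this formula f = 0.15 corresponds to a between-arm difference in mean change of 0.6 SD: 0.6/√(4/128) = 3.39, and 3.39² ≈ 11.5. The power figures below carry that reading; the variance factors do not depend on it.

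**2. What adjustment does.** With two visits and complete data, the time-by-group coefficient is the difference between arms in mean change.

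- *Main effect of gestation only.* It shifts both visits equally and cancels from the change. In simulated fits of the random-intercept model (25 data sets at each of r = 0 and r = 0.3), the time-by-group estimate moved by less than 1e-14 and its standard error did not change materially.
- *With the gestation-by-time term.* The variance is multiplied by about (1 − r²)(N − 3)/(N − 4), and one degree of freedom is used. Here r is the within-arm correlation of entry gestation with ISI change. At N = 128, (N − 3)/(N − 4) = 125/124 = 1.008.

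| r (assumed) | Variance factor | Power at 128 | N for 80% |
|---|---|---|---|
| no gestation term | 1 | 78.0% | 134 |
| 0 | 1.008 | 77.6% | 136 |
| 0.1 | 0.998 | 78.1% | 134 |
| 0.2 | 0.968 | 79.6% | 130 |
| 0.3 | 0.917 | 82.1% | 124 |

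Break-even is at |r| of about 0.095. The mixed-model fits agree: the mean standard error fell from 0.177 to 0.171 at r = 0.3 and rose from 0.179 to 0.180 at r = 0.

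**3. What r might be.** The documents give nothing, so this is illustration only. Suppose entry is uniform from 6–12 weeks up to 28 weeks (SD = range/√12 = 4.6 to 6.4 weeks), ISI change has SD 5, and change varies by 0.15 points per week of entry gestation. Then r = 0.15 × 4.6/5 = 0.14 to 0.15 × 6.4/5 = 0.19. The saving, 128/(1 − r²) − 128, is about 2.5 to 5 women. Reaching r = 0.3 would need a slope of 0.3 × 5/6.4 = 0.23 to 0.3 × 5/4.6 = 0.33 points per week.

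**The case against.** The strongest reply is that nothing here is wrong. Allocation is concealed and randomized, so the comparison without covariates is unbiased and has valid type I error. Leaving out a covariate contradicts nothing in the plan. That stands, and it limits the point to efficiency.

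Four stronger readings are tempting, and the documents support none of them.

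- **A chance imbalance in gestation distorts the effect.** It is already part of the standard error. On the illustrative inputs above, with 64 per arm, the standard error of the difference in change is 5 × √(2/64) = 0.88, a 95% range of ±1.73 points. The part due to gestational imbalance is at most 1.96 × 0.15 × 6.4 × √(2/64) = 0.33 points. Removing it leaves √(1.73² − 0.33²) = ±1.70.
- **Adjustment is a free gain.** The documents report no relation between entry gestation and ISI change. If there is none, adjustment costs about 0.4 points of power.
- **The baseline tests damage the analysis.** Under randomization they answer no useful question, but Statistical methods attaches no consequence to them, so the primary result is unaffected. That they would prompt adjustment chosen after seeing the data is conjecture.
- **One linear gestation-by-weeks term serves every model.** It does not suit visits that may fall on either side of delivery.

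It is also fair to say that gestation is probably not the most valuable covariate. Adjusting for baseline ISI, or constraining the arms to a common baseline mean, would cut the variance from 2(1 − ρ) to 1 − ρ². At ρ = 0.5 that is from 1 to 0.75, about what r = 0.5 for gestation would give (factor 0.756). This can be done as well as the change proposed here.

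**Conclusion.** The point holds as an optional, low-cost improvement in precision. The documents confirm wide entry gestation, no named stratification factor, and models without gestational age. They do not show that gestation predicts change in ISI, so the size of the gain is unknown. Over r from 0 to 0.3, power at 128 evaluable women runs from 77.6% to 82.1%, against 78.0% unadjusted.

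Those figures assume two visits, ρ = 0.5, f = 0.15, complete data and a linear relation with gestation. The conclusion that the time interaction is essential rests only on the two-visit structure. The argument is stronger for the later visits, where entry gestation fixes the timing relative to delivery, but no gain can be quantified there from the documents.

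**What to change.** In Statistical methods, before unblinding, prespecify the following:

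1. In the primary baseline-to-10-week model and the matching secondary models, include gestational age at randomization (continuous) and its interaction with time. State that both terms are needed, because the main effect alone leaves the two-visit contrast unchanged.
2. In models that include later visits, interact gestational age with visit as a category, not with linear weeks.
3. Optionally, replace the baseline t-tests and chi-square tests with a descriptive table by arm. This does not alter the primary result.

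The cost is a sentence or two and no new data: gestation reported at screening can be carried forward to the date of randomization. The primary contrast loses one degree of freedom, and at worst about 0.4 points of power if gestation is unrelated to change.
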